7.3.2 Prognostic variables

Prognostic indices will be calculated for DLBCL patients, MCL patients, and FL patients. No prognostic index will be calculated for other indolent NHL patients. Details of the prognostic indices used are given below.

7.3.2.1 Prognostic variables for DLBCL patients

The International Prognostic Index (IPI) [5] will be calculated for all DLBCL patients. This is calculated from the following items:

- Age older than 60
- Lactate dehydrogenase level higher than normal
- ECOG performance status score of 2 or greater
- Stage III or IV disease
- More than one involved extranodal disease site

The IPI gives one point for each of the above characteristics, for a total score ranging from zero to five correlating with the following risk groups :

- Low risk: 0–1 points
- Low-intermediate risk: 2 points
- High-intermediate risk: 3 points
- High risk: 4–5 points

The categories above will also be collapsed into low risk (0–2 points) and high risk (3–5 points). Subgroup analysis according to low risk and high risk IPI scores will be presented for DLBCL patients for the outcomes of overall response rate and PFS.

7.3.2.3 Prognostic variables for FL patients

The Follicular Lymphoma International Prognostic Index (FLIPI) [7] will be calculated for all FLIPI patients. This is calculated taking into account the following factors:

- Age > 60
- Serum LDH > ULN
- Hgb < 12 g/dl
- Stage III or IV
- Number of nodal sites > 4

The presence of ≤ 1 , 2, and ≥ 3 factors define low, intermediate, and high risk.

The categories above will also be collapsed into low risk (0–2 points) and high risk (≥ 3 points). Subgroup analysis according to low risk and high risk FLIPI scores will be presented for FL patients for the outcomes of overall response rate, PFS, and OS.

7.3.3 Immunogenicity

Patient has positive anti-MOR00208 antibodies (yes/no/missing) by visit:

- yes, if a titer is available
- no, if result is reported as negative
- missing, if anti-MOR00208 measurement is not available

Patient has developed positive anti-MOR00208 antibodies during study (yes/no/transient/not evaluable/missing):

- yes, if the patient has at least one positive post-baseline sample containing positive anti-MOR00208 antibodies including a positive result for the last sample analyzed; baseline sample has to be tested negative
- no, if baseline as well as all post-baseline results are negative
- transient, if the patient has at least one positive post-baseline sample containing positive anti-MOR00208 antibodies but a negative result for the last sample analyzed; baseline sample has to be tested negative
- not evaluable, if the baseline sample of the respective patient was tested positive
- missing, if no post-baseline anti-MOR00208 measurement is available

7.3.4 Efficacy

7.3.4.1 Investigator Assessment

The Investigator will assess tumor response at specific study visits according to the criteria for NHL as defined in Section 17.4 of the study protocol. All of the criteria are based on the revised IWG response criteria [4].

The categories of overall tumor response assessment of the Investigator are as follows:

- CR - Complete remission
- PR - Partial remission
- SD - Stable disease

- PD - Progressive disease
- Missing (if response assessment is not done)

In case of progressive disease, the date of progression is given by the Investigator. In case any anti-tumor treatments other than MOR00208 are given before end of study (see also section 8.3), it is regarded as protocol non-compliance. Following a conservative approach, tumor assessments of the Investigator after start of other anti-tumor treatment which are non-PD will not be taken into account for any of the derived efficacy variables described below, whereas assessments of PD will still be taken into account. This ensures that a progression is still included in the analysis if an anti-tumor treatment has been started based on clinical progression, but the image confirming PD was done at a later time point. A response assessment provided by investigator after start of other than protocol indicated anti-tumor treatment will, however, not be counted for overall best response.

Tumor Response categories (Investigator) will be evaluated in terms of absolute and percentage frequencies by visit.

Overall best response (Investigator) will be defined as best response across the following time points: end of the second, end of third cycle, during a response assessment in the follow-up period or at an unscheduled assessment after end of second cycle.

Overall response rate (ORR) (Investigator) will be evaluated as the rate of patients who met the criteria of PR or CR at the end of either the second or third cycle or during a response assessment in the follow-up period (i.e. who have an overall best response of PR or CR).

Overall rate of SD (disease control rate) (Investigator) will be evaluated as the rate of patients who met the criteria of PR, CR or SD at the end of either the second or third cycle or during a response assessment in the follow-up period (i.e. who have an overall best response of PR, CR or SD).

Duration of response (Investigator): Duration of response will be defined as the time from date of first response (CR or PR) until first date that recurrence or progressive disease is objectively documented. The duration of response will be calculated in the subgroup of all patients showing any response; confirmation of response will not be required. Patients who showed a response but did not show PD or recurrence until end of study or before study discontinuation (i.e. patients who are at least stable at their last tumor assessment) are considered censored at the timepoint of last response assessment. Deaths due to causes other than progression of disease are to be reported as SAEs and are censored for duration of

Statistical Analysis Plan Final Version 4.0

response analysis at the date of last tumor assessment before death. The cause of death has to be recorded as free text by the Investigator on the eCRF study completion page. If the cause of death does not explicitly state whether death is related to progression of disease, a query will be raised to ask the investigator to classify the relationship to disease (yes/no). Morphosys Drug Safety will assess the causality of the SAE by reviewing the corresponding SAE documents.

Time to response (Investigator): Time to response will be defined as the time from Cycle 1, Day 1 (first administration of study drug) until the date of first response (CR or PR). Patients who do not have a response to treatment will be censored at the date of their last tumor assessment.

Time to progression (Investigator): Time to progression is defined as the time from Cycle 1, Day 1 (first administration of study drug) until date of first tumor progression (which is entered in the tumor assessment module). Patients who do not show any documented progression (which is entered in the response assessment module of the eCRF) before the end of study or before study discontinuation or before death are considered censored using the last date with a tumor assessment as censoring date (irrespective of when the patient died). Deaths due to causes other than disease progression are censored.

Progression-free survival (Investigator): Progression-free survival is defined as the time from Cycle 1, Day 1 (first administration of study drug) until date of first tumor progression (which is entered in the response assessment module of the eCRF) or date of death from any cause. If the patient does not show any documented progression (which is entered in the tumor assessment module) before death, the date of progression will be the date of death if death occurs within 2 months after the last date with a tumor assessment. If death occurs after 2 months after the last date with a tumor assessment or the patient did not progress or die until end of study or before withdrawal, the patient will be analyzed as censored using the last date with a tumor assessment as censoring date.

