⁹ Results from bone marrow examination done within 4 weeks before screening are acceptable, if the patient's disease has been stable since then. In this case, obtaining bone marrow samples for the sole purpose of CD19 expression does not need to be repeated.

¹⁰ Bone marrow examinations should only be repeated if response at last bone marrow examination was not CR.

¹¹ Including body height at screening only. Physical examination includes palpable tumor assessment, general appearance, skin, head, eyes, ears, nose, throat, lungs, breasts and axillae (if applicable including bi-dimensional measurement of cervical, supraclavicular, axillary and inguinal lymph nodes), cardiovascular system, back and spine, abdomen (if applicable including spleen size below the costal margin), extremities, infusion site, lymph nodes, and neurological examination.

¹² Physical examination will be used for response assessment.

¹³ Immediately before infusion; 15, 30, and 60 minutes during infusion; at end of infusion; and every hour for two hours after completion of infusion.

¹⁴ Performed 1 hour \pm 10 minutes post dose. Additionally, for Cycle 1 Day 1 predose; 12-lead ECG recording should include determination of heart rate and RR, PR, QRS, QT, and QTc intervals. The 12-lead ECG will be recorded after 5 minutes of rest in a supine position.

¹⁵ For all patients neck/chest/abdomen/pelvis CT is required. PET should also be performed for response assessment if tumor was PET avid at baseline.

¹⁶ Radiographic examinations in addition to the neck/chest/abdomen/pelvis CT/PET evaluations are to be done, as appropriate. (For MRI, please see Section 10.6.) Follow-up radiographic examinations will be performed at the end of Cycle 2, Cycle 3, and at the second and subsequent follow-up visits for any procedures performed at baseline visit.

¹⁷ Radiographic evaluations may be performed up to 3 days before the scheduled visit during Cycle 1-3 and within +/- 4 days of the planned visit during follow-up. If a patient discontinues from the study before a response assessment, an evaluation will occur approximately one month after the patient discontinues from the study. CT/PET examinations that were done up to 3 weeks before Cycle 1 Day 1 may be used as a patient's baseline assessment. (For MRI, please see Section 10.6.)

¹⁸ Anti-MOR00208 sample will be taken at third follow-up visit only.

¹⁹ Sample to be taken and evaluated before study drug administration.

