14.4 Primary Objective

The primary efficacy endpoint will be ORR as determined by using revised IWG response criteria for malignant lymphoma. The final ORR for each subtype will be the rate of patients who met the ORR definition at the end of either the second or third cycle or during the follow-up period (best response). The denominator for calculating the rate will be based upon the total number of patients in the ITT population, thus patients without any postbaseline assessment of NHL response will be included as nonresponders. Overall ORR, independent of NHL subtype, will also be summarized; 95% CI for ORR for each subtype and over all subtypes will be summarized.

All efficacy analyses will be provided for the ITT Population.

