7.3.4.2 Central Read

Additionally a central radiology read of scans will be performed by SYNARC/BioClinica. The revised IWG criteria definitions [4] will also be applied. Details of the central read are described in the Independent Review Charter, Version 1.0, 01-JUL-2013, provided by SYNARC.

The independent reviewers (two primary radiologists) will be presented with all time points sequentially in chronological order, and will provide assessments for each time point. For the

overall tumor assessment of the central read a slightly different terminology is used:

- CR - Complete response
- PR - Partial response
- SD - Stable disease
- PD - Relapsed or progressive disease
- NE - Non-Evaluable (can be applied if repeated measurements cannot be applied for reasons such as inadequate or missing imaging and when progression/relapse cannot be assigned for the visit overall response)
- ND - No Disease (this category is used if there is no tumor and there was no tumor at baseline)

Once the independent reviews for all time points in the course of the study have taken place, all time points for a particular patient will be again reviewed together by the two independent reviewers in a global patient review over all time points. In their global patient review the two independent reviewers will determine:

- best overall response (defined as best response the subject had since treatment started taking into account scheduled and unscheduled visits)
- date of the best overall response
- duration of best overall response (calculated by the system as time from first response to progression if patient is PD at a specific visit)
- date when progression/relapse occurred

Finally, an adjudicator radiologist will perform adjudication, in case there is any discrepancy in the global patient review of the two primary radiologists. The adjudicator will review both initial readings and will record a new review that will agree with either of the duplicate reviews. Thus, the adjudicator will need to agree to the complete reading of one of the primary radiologists (all assessments by visit and all variables from corresponding global review). A mandatory comment will need to be recorded. The adjudicated reading results will be considered as the results for the involved patients.

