9.1 Primary Efficacy Analysis

The primary efficacy endpoint will be ORR as determined by the Investigator by using revised IWG response criteria for malignant lymphoma [4]. The final ORR for each subtype will be the rate of patients who met the ORR definition at the end of either the second or third cycle or during the follow up period (best response) (i.e the ORR will be derived from the variable “overall best response”). The denominator for calculating the rate will be based upon the total number of patients in the ITT population, thus patients without any post baseline assessment of NHL response will be included as non-responders. Overall ORR, independent of NHL subtype, will also be summarized. Exact (Clopper-Pearson) 95% CIs for ORR for each subtype and over all subtypes will be presented.

In addition, the tumor response categories will be evaluated by visit. The corresponding number of patients in each of the response categories will be summarized in a frequency table by visit. In this summary all patients who had discontinued will be analyzed as missing for all visits after study discontinuation, also accounting for all patients in the ITT population in the denominator.

ORR will be also calculated and respective results provided based on the central review assessment (based on the variable “best overall response”).

Sensitivity analysis:

The ORR will be calculated only considering patients who had at least on post-baseline response assessment. The analysis will be done using the local (investigator) assessment, and also based on the central review assessment.

Concordance rate:

The concordance rate in terms of response assessment represents the agreement in the best overall response between the central read and investigator assessment. The concordance rate is the number of patients that are concordant over the total number of patients assessed, and will be calculated across all response categories. A confusion matrix will be generated. The

concordance rate is calculated by adding the diagonal counts and dividing by the total number of patients assessed. Moreover, the agreement (%) of the investigator assessment with the central read in terms of best ORR will be calculated (i.e., the total number of patients with a best response of CR or PR by central review divided with the total number of patients with a best response of CR or PR by investigator assessment multiplied by 100).

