Patients without any post-baseline response assessment will be considered as not evaluable (NE) in both the central read and investigator assessment. Patients who have been evaluated by investigator assessment, but not by central review assessment will be excluded from the concordance analysis.

The proportion (%) of patients who had at least one central review among the total number of patients who underwent at least one investigator assessment will be calculated. Moreover, the proportion (%) of the total number of central reviews among the total number of investigator assessments will be derived (i.e., the total number of central reviews across all visits and all patients divided with the total number of investigator response assessments across all visits and all patients multiplied by 100). The analysis will be conducted using the ITT population.

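### The investigator–central concordance rate compares best responses taken over different windows and counts patients with no assessment as agreement

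*SAP*

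**What the plan says.** **Investigator read.** SAP 7.3.4.1 states: "Overall best response (Investigator) will be defined as best response across the following time points: end of the second, end of third cycle". It then adds findings "during a response assessment in the follow-up period or at an unscheduled assessment after end of second cycle". SAP 9.1 derives the primary ORR from this variable. Protocol 14.4 sets the same anchor, with response counted "at the end of either the second or third cycle or during the follow-up period (best response").

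**Central read.** SAP 7.3.4.2 defines best overall response as the "best response the subject had since treatment started taking into account scheduled and unscheduled visits". Central ORR is built on it.

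**Comparison.** SAP 9.1 places the two best responses in a confusion matrix across all response categories, adds the diagonal counts, and divides by the number of patients assessed. It then says: "Patients without any post-baseline response assessment will be considered as not evaluable (NE) in both the central read and investigator assessment". Patients evaluated by the investigator but not centrally are excluded. There is no rule for the reverse case.

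**Early discontinuation.** Protocol Table 2, footnote 17, says that for a patient who leaves before a response assessment "an evaluation will occur approximately one month after the patient discontinues from the study". Protocol 10.6 repeats this, qualified by whether it is possible.

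**The concern.** The concordance rate is the plan's summary of how far the local reading of an open-label trial matches the independent reading. Two features stop it from measuring that.

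First, the windows differ. A patient scanned only before the end of Cycle 2 can hold a central category while having no clear investigator category. Any resulting disagreement reflects the definitions and not the readers.

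Second, patients whom nobody assessed are given the same label in both reads. Summed on the diagonal, they raise the rate without any judgement having been made.

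The two effects run in opposite directions, so the published figure could not be corrected by eye.

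**Working it through.** **1. Which scans fall in the gap.** Protocol Table 2 schedules no response imaging between baseline and Cycle 2 Day 28, so only unscheduled and post-discontinuation scans matter. Two 28-day cycles end nominally on Day 56. Taking one month as about 30 days, a post-discontinuation scan precedes that date if the patient leaves the study before about Day 56 − 30 = Day 26. Leaving on Day 15 or Day 22 gives a scan at about Day 45 or Day 52.

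**2. Whether another investigator time point covers it.** Protocol 9.6 and 9.10 send patients who discontinue before the end of Cycle 2 to the End of Study visit. Protocol 10.3 describes follow-up for patients who had Cycle 3; 9.6 and 9.10 add those with at least SD at the end of Cycle 2 who have not progressed. The scan is therefore not clearly a follow-up assessment. The SAP does not say whether the end of the second cycle is a calendar day or a completed cycle. The non-responder rule in SAP 9.1 names only patients with no post-baseline assessment, and this patient has one.

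**3. Size for ORR.** The plan's own figure reproduces: the Clopper-Pearson lower limit for 9/30 is 14.7%. If one of nine responders were not counted (assumption), 8/30 = 26.7% with lower limit 12.3%, a fall of 1/30 = 3.3 points in the estimate. An early PD scan changes nothing here, because the patient is a non-responder either way.

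**4. Size for the comparison, window effect alone.** With that one responder counted only centrally in a cohort of 30, the highest possible concordance is 29/30 = 96.7%. The second agreement measure in SAP 9.1 (central CR/PR count divided by investigator CR/PR count) becomes 9/8 = 112.5%.

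**5. Size for the comparison, unassessed patients.** Let *a* be agreement among assessed patients, *u* the number with no assessment and *N* the total. If NE–NE counts as agreement:

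reported rate = [*a*(*N* − *u*) + *u*] / *N* = *a* + (1 − *a*)·*u*/*N*

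The documents give none of these inputs. With *N* = 90 assumed:

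| *a* | *u* = 10 | *u* = 20 |
|---|---|---|
| 60% | (48 + 10)/90 = 64.4% | (42 + 20)/90 = 68.9% |
| 80% | (64 + 10)/90 = 82.2% | (56 + 20)/90 = 84.4% |

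The inflation is larger when true agreement is lower.

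**The case against.** **The investigator window is deliberate.** A reader might infer that the primary ORR is wrong because it discards response scans. The documents do not support that. The synopsis measures ORR after two cycles of treatment, and Protocol 14.4 and SAP 2.2.1, 7.3.4.1 and 9.1 all anchor response at the end of Cycle 2 or later. Patients who leave early stay in the ITT denominator, so the choice is conservative. Widening it in an SAP dated April 2019, for an analysis with a cutoff foreseen in July 2015, could only raise an open-label response rate. This objection stands.

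**The path to a lost responder is narrow.** The scan is timed from leaving the study, not from the last dose. Under the 15-day toxicity rule, a patient last dosed on Day 8 whose Day 15 dose is postponed leaves after about Day 30 and is scanned around Day 60. One last dosed on Day 15, with the Day 22 dose postponed, leaves after about Day 37 and is scanned around Day 67. Both could qualify as unscheduled assessments after Cycle 2. A lost responder must leave by about Day 26, be in CR or PR a month later, be scanned before Day 56, and have started no other anti-tumor treatment. This also stands, and the SAP wording is ambiguous, not a settled exclusion.

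**Early progressors.** It is tempting to say that they are lost from the efficacy results. They are not: TTP and PFS run from Cycle 1 Day 1 without this window. Only the best-response table and the confusion matrix could change.

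**The concordance denominator.** SAP 9.1 divides by patients assessed, which could be read as leaving out those with no assessment. On that reading, however, assigning them NE in both reads has no purpose, particularly as the same paragraph explicitly excludes investigator-only patients. The confusion matrix would show an NE–NE cell, but the headline rate would still include it. This objection shows a need for repair, not that the rule is harmless.

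**Conclusion.** The point holds for the comparison of the two reads. Their best responses are defined over different windows and compared without alignment, and the rule for unassessed patients most naturally counts them as agreement. Under the assumed inputs the second effect adds 2.2 to 8.9 points to the concordance rate. The window effect works the other way and is probably small, because no imaging is scheduled before the end of Cycle 2. The true counts of early scans and unassessed patients are not in the documents.

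The point does not extend to calling the primary ORR misdefined. Its window is stated consistently. What is missing is a statement of where the post-discontinuation scan belongs.

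**What to change.** - **SAP 9.1, concordance.** Compute the rate and the confusion matrix only in patients with at least one post-baseline assessment by both reads, using the same assessment window for both. Report separately the number with no assessment.
- **SAP 7.3.4.1, mapping.** Keep the primary ORR window. State whether the scan about one month after early discontinuation counts as a follow-up or an unscheduled assessment, and whether the end of the second cycle is a calendar day or a completed cycle.
- **SAP 9.1, sensitivity.** Add an investigator ORR using all assessments from first dose until first PD or start of other anti-tumor treatment.

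No new data are needed. The cost is some text, reprogramming and one extra table, and the concordance rate may come out a few points lower.

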Duration of best overall response (Central Read): Duration of best overall response will be defined as the time from date of best overall response (as provided by the central reviewer) until first date that recurrent or progressive disease is objectively documented. The duration of

Statistical Analysis Plan Final Version 4.0

best overall response will be calculated in the subgroup of all patients showing any response; confirmation of response will not be required. Patients who showed a response but did not show PD or recurrence until end of study or before withdrawal (according to the central reviewer) are considered censored at the timepoint of last response assessment. Deaths without documented progression before death (according to the central reviewer) are also considered as censored at date of last response assessment.

Time to response (Central Read): Time to response will be defined as the time from Cycle 1, Day 1 (first administration of study drug) until the date of best overall response (as provided by the central reviewer) if best overall response is PR or CR. Patients who do not have a response to treatment will be censored at the date of their last tumor assessment.

Time to progression (Central Read): Time to progression is defined as the time from Cycle 1, Day 1 (first administration of study drug) until date of progression/relapse (as provided by the central reviewer). Patients who do not show any documented progression (according to the central reviewer) before the end of study or before withdrawal or before death are considered censored using the last date with a tumor assessment as censoring date (irrespective of when the patient died).

Progression-free survival (Central Read): Progression-free survival is defined as the time from Cycle 1, Day 1 (first administration of study drug) until date of progression/relapse (as provided by the central reviewer) or date of death from any cause (as given in the eCRF). If the patient does not show any documented progression before death (according to the central reviewer), the date of progression/death will be the date of death if death occurs within 2 months after the last date with a tumor assessment. If death occurs after 2 months after the last date with a tumor assessment or the patient did not progress or die until end of study or before withdrawal, the patient will be analyzed as censored using the last date with a tumor assessment as censoring date.

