9. EFFICACY ANALYSES

All efficacy analyses will be provided for the ITT Population. All efficacy analysis will be done using both the central radiology and local (i.e., investigator) assessment. Kaplan-Meier plots will be generated for all time-to-event analyses (i.e., for the Time to Progression, Progression-Free Survival, Duration of Response).

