9.2 Secondary Efficacy Analysis

All secondary efficacy analyses will be provided twice, based on the response assessment of the Investigator and based on the central review assessment.

The analysis of ORR as described in section 9.1 will be additionally be stratified by Fc γ RIIIa and Fc γ RIIa polymorphism.

Fc γ R subgroups will comprise the heterozygous population and each different homozygous population, as well as the combined heterozygous plus low affinity homozygous Fc γ R populations. Subgroups with fewer than five patients will not be analysed.

These stratifications will be done for the overall analysis population as well as by NHL subtype.

The overall stable disease rate will be analyzed analogously to the overall response rate as described in Sect. 9.1.

Time to progression and progression-free survival will be analyzed using Kaplan-Meier methods. Kaplan-Meier tables for progression-free survival and time to progression will contain number of patients, number of patients with an event (non-censored patients), percentage of patients with an event, median time [months], 25% and 75% quantile and 95%-

confidence intervals for median (Brookmeyer and Crowley, 1982).

Moreover, the percentage of patients having an event until 2, 4, 6, and 12 months together with the corresponding 95%-confidence intervals will be retrieved.

In the main analysis of PFS, only patients with radiologically confirmed progression or death within 2 months of the last radiological assessment will be counted as having had a PFS event. A sensitivity analysis will also be done in which patients who were withdrawn from the study because of disease progression will be included as having a PFS event, even in the absence of radiological confirmation of disease progression.

Duration of response and time to response (Investigator) and duration of best overall response and time to response (Central Read) will also be analyzed using Kaplan-Meier estimates for median, 25% and 75% quantile. The analysis of duration of response will be restricted to the subgroup of responders. Moreover, the percentage of patients having an event after 2, 4, 6, and 12 months together with the corresponding 95%-confidence intervals will be retrieved from the Kaplan Meier curve.

The analysis of duration of response and time to response will be presented for all responders overall.

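### Time to response: the SAP censors non-responders in one section and presents responders only in another; if ITT patients enter the Kaplan-Meier curve, it can overstate the chance of response

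*SAP*

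**What the plan says.** SAP 7.3.4.1 measures time to response from the first dose to the first CR or PR and adds: "Patients who do not have a response to treatment will be censored at the date of their last tumor assessment". SAP 7.3.4.2 repeats the censoring rule for the central read but places the event later in some patients, because time runs "until the date of best overall response (as provided by the central reviewer) if best overall response is PR or CR".

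SAP 9.2 says that duration of response and time to response "will also be analyzed using Kaplan-Meier estimates for median, 25% and 75% quantile". The same paragraph asks for "the percentage of patients having an event after 2, 4, 6, and 12 months together with the corresponding 95%-confidence intervals", read from the Kaplan-Meier curve, and 9.2 also lists a Kaplan-Meier plot of time to response. No competing-risk method is named.

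Three statements bear on which patients enter the analysis:

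- SAP 9, opening: "All efficacy analyses will be provided for the ITT Population".
- SAP 9.2: "The analysis of duration of response will be restricted to the subgroup of responders". This names duration of response only.
- SAP 9.2, next paragraph: "The analysis of duration of response and time to response will be presented for all responders overall".

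**The concern.** Kaplan-Meier censoring assumes that a censored patient could still have the event later, at the same rate as those who remain under observation. A patient who progresses cannot. The protocol synopsis (statistical methods) discontinues patients with PD after the second cycle and counts them as non-responders, and Protocol 10.3 continues follow-up only until relapse. SAP 7.3.4.1 also disregards responses seen after other anti-tumor treatment has started. Censoring these patients shrinks the risk set without using up any response probability, so each later response is given too much weight.

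Later responses are possible under this design. Patients with SD go on to Cycle 3, and the ORR counts responses at the end of Cycle 3 and in follow-up.

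At stake is a descriptive table and plot that could show a response probability by month above the trial's own ORR, and a median time to response that most patients never reach.

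**Working it through.** **The plan's own figures.** The documents state no time-to-response percentage. The design figures in SAP 5 reproduce: the probability of fewer than 2 responses in 10 at a 30% ORR is 0.7^10 + 10(0.3)(0.7^9) = 0.149, and the exact lower 95% limit for 9/30 is 14.7%.

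**Inputs from the documents.** Cohort of 30, ORR 30% (9 responders). Nominal response visits, from Protocol 10.2 and 10.3:

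- Cycle 2 Day 28 = day 56.
- Cycle 3 starts 14 days after Cycle 2 Day 22 (day 50), so on day 64; Cycle 3 Day 28 = day 91.
- Follow-up visit 2 = 91 + 28 + 42 = day 161.
- Visit 3 (day 203) has no response assessment; visits 4 and 5 fall at about days 294 and 385.

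Divided by 30.4375 (SAP 7.1), these are 1.8, 3.0, 5.3, 9.7 and 12.6 months.

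**Inputs assumed.** The timing of responses and of last assessments in non-responders is not in the documents. Patients never assessed are taken as leaving the risk set before the first visit.

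**Formulas.** One minus Kaplan-Meier = 1 − Π(1 − d/n), with d responses among n at risk at each visit. Cumulative incidence with progression and death as competing events = responders to date / 30, if nobody is censored administratively earlier.

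**One case in full.** Responses 5, 2, 1, 1 at the first four visits; non-responders censored 12, 4, 3, 1, 1 at the five visits. The numbers at risk at the first four visits are 30, 13, 7 and 3.

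- By 2 months: 1 − 25/30 = 16.7%; cumulative incidence 5/30 = 16.7%.
- By 4 months: 1 − (25/30)(11/13) = 29.5%, against 7/30 = 23.3%.
- By 6 months: multiply the survival by 6/7, giving 39.6%, against 8/30 = 26.7%.
- By 12 months: multiply by 2/3, giving 59.7%, against 9/30 = 30.0%. A median of 294 days would be reported.

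**Range over assumed timings** (9 responders of 30; entries are one minus Kaplan-Meier against cumulative incidence):

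| Responses by visit | Non-responders' last assessment | 6 months | 12 months |
|---|---|---|---|
| 9,0,0,0,0 | 12,4,3,1,1 | 30.0% v 30.0% | 30.0% v 30.0% |
| 9,0,0,0,0 | 3 never assessed; 11,4,2,1,0 | 33.3% v 30.0% | 33.3% v 30.0% |
| 7,2,0,0,0 | 6,4,4,4,3 | 32.4% v 30.0% | 32.4% v 30.0% |
| 6,2,1,0,0 | 12,4,3,1,1 | 44.4% v 30.0% | 44.4% v 30.0% |
| 3,2,2,1,1 | 12,4,3,1,1 | 39.3% v 23.3% | 54.5% v 26.7% |
| 5,2,1,1,0 | 12,4,3,1,1 | 39.6% v 26.7% | 59.7% v 30.0% |
| 5,2,1,1,0 | 3 never assessed; 11,3,2,1,1 | 44.4% v 26.7% | 63.0% v 30.0% |

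**A second set.** Take 100 patients with 30 responders, and non-responders last assessed 45, 15, 5, 5 at days 56, 91, 161, 294. Only the split of responses over days 56, 91 and 161 changes. At 6 months:

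- 30/0/0: 1 − 70/100 = 30.0%.
- 27/3/0: 1 − 0.73(25/28) = 34.8%.
- 24/4/2: 1 − 0.76(27/31)(10/12) = 44.8%.
- 20/5/5: 1 − 0.80(30/35)(10/15) = 54.3%, with a reported median of 161 days.

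The true proportion is 30% each time. Only the last split yields a median.

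**The responders-only reading.** With responses 5, 2, 1, 1 the curve gives 5/9 = 55.6%, 7/9 = 77.8%, 8/9 = 88.9% and 100% at 2, 4, 6 and 12 months. Nobody is censored. It describes timing among responders and is not a response rate.

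**The case against.** The strongest reply is that SAP 9.2 already presents time to response for responders. On that reading no non-responder is in the curve and the bias does not arise. This stands as one legitimate reading, but it does not settle the matter. A responders-only analysis leaves the censoring sentences in 7.3.4.1 and 7.3.4.2 without purpose, and 9.2 expressly restricts duration of response to responders without doing the same for time to response. A programmer could follow either text.

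Second, the monthly percentages come directly after the sentence on duration of response and might be meant for that variable alone. That is possible. The paragraph opens with both variables, so covering both is the more natural reading, and the median, quartiles and plot apply to time to response in any case.

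Third, the large figures need late responses. In the 54.3% example, 5 of the 15 patients still at risk (33%) respond at day 161, against 20 of 100 at the first visit. Maintenance requires at least PR at the end of Cycle 3, so patients not yet in response would have had their last dose at about day 85 (day 64 + 21). This objection holds: a reader might infer that the reported percentages must far exceed the true response rate, and the documents do not support that. Scenarios with mostly early responses show little or no excess.

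Fourth, the practical reach is limited. The ORR is a simple ITT proportion with an exact interval (SAP 9.1) and is not read from this curve. The Stage 1 rule uses counts of responders. Time to response is not among the secondary endpoints in SAP 2.2.2, and Protocol 14.10 plans no inferential testing. All of this stands and lowers the severity.

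**Conclusion.** Two things hold. The SAP gives incompatible instructions on which patients enter the time-to-response analysis. And if ITT patients enter, censoring those who progressed or died lets one minus Kaplan-Meier overstate the response probability whenever a response follows the censoring of such a patient.

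At a 30% ORR the excess in the assumed scenarios runs from none to about 24 points at 6 months (54.3% against 30%). At 12 months it reaches about 30 points (59.7% against 30.0%, or 33.0 points if three patients are also never assessed). These sizes rest on assumed timing; the later figures come from very small risk sets (three patients at day 294 in the worked case). For the central read, dating the event at best rather than first response can push events later and enlarge the excess.

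It would go too far to say that the plan will report inflated response rates or that the primary result is at risk. The defect is an unsettled analysis set plus a censoring rule that is unsuitable under one of its readings. Severity is low to moderate.

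**What to change.** State one analysis set for time to response in SAP 7.3.4.1, 7.3.4.2 and 9.2. There are two coherent options:

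1. **Responders only.** Summarise time to response descriptively (median, range) and delete the non-responder censoring sentences from 7.3.4.1 and 7.3.4.2. Drop the Kaplan-Meier plot, or label it as timing among responders.
2. **ITT curve.** Use cumulative incidence of response, with progression and death without response as competing events. Keep censoring for patients still followed without response at the data cut-off.

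In either case, say whether the 2-, 4-, 6- and 12-month percentages apply to time to response or only to duration of response.

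The first option is the simpler and agrees with the responders sentence already in 9.2. The cost is a few sentences of SAP text and one revised table and plot. No data collection, sample size or primary analysis changes.
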